Protocol Synopsis

Study Title & ID	I ntravascular Ultrasound- G uided Intervention for Venous Leg U lcers (IGuideU) Protocol ID: 200202
Objectives	
The primary objective of this study is to determine whether the interrogation of the deep venous system (iliac-common femoral veins) for deep venous obstruction (DVO) by multiplanar venography (MPV) plus intravascular ultrasound (IVUS), with subsequent interventional treatment determined and guided by IVUS (interrogation group), results in improved clinical outcomes when compared to deferred interrogation of the deep venous system (deferred-interrogation group).
 
The secondary objectives are to assess changes in treatment decision parameters made with MPV after further investigation with IVUS and to assess the long-term clinical and economic impact of IVUS-guided interventional treatment for venous leg ulcers compared to the deferred-interrogation group.

Study Design	
Global, prospective, multi-center, randomized controlled trial. After signing a written informed consent, patients will be randomized 1:1 to either a deferred-interrogation group or to an interrogation group in which patients will be first evaluated with MPV imaging during iliac-common femoral vein assessment for possible endovascular intervention and then further interrogated with IVUS imaging. The treatment plan derived from venography alone will be compared to the treatment plan created with the addition of the IVUS information and any differences in treatment plan will be documented. Confirmation of whether or not the threshold of stenosis/occlusion required for endovenous stenting has been met will be determined by the IVUS imaging obtained. Any patients determined to require venous stenting will be stented according to the on-label manufacturer’s instructions for the use of IVUS in guiding stent sizing and placement.
 
This study will employ an independent core laboratory to evaluate, review and adjudicate all scheduled and unscheduled de-identified wound, MPV, and IVUS images. The study will also utilize a medical monitor to review and adjudicate peri-procedural serious adverse events (SAE).

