
Test Groups
	
 • Deferred-Interrogation Group: See guidelines below. • Interrogation Group: Compression therapy plus endovascular imaging (MPV+IVUS) with or without intervention (stenting). 
The deferred-interrogation group will continue to receive non-invasive therapies consisting primarily of compression therapy/stockings that would have otherwise been continued outside of this research protocol. Listed below are the protocol guidelines for deferred-interrogation therapies:
 
Mandate
 
 • Continued compression therapy/dressing as prescribed. 
Allow
 
 • Periodic leg elevation. • Sclerotherapy under ulcer bed. • Recommend mechanical debridement as needed. • Wound biopsy if evidence of infection. • Systemic antibiotics if patient is diagnosed with an infection, avoid prophylactic prescription. • Pain management medication (Pentoxifylline/Trental) allowed but not recommended • Topical antimicrobial as needed. 
Prohibit
 
 • Negative pressure systems. • Artificial and/or autologous skin grafting within first 3 months after randomization and within the first 3 months for subjects that crossover from the deferred-interrogation group to the interrogation group. • Skin substitutes and tissue-based therapies within first 3 months after randomization and within the first 3 months for subjects that crossover from the deferred-interrogation group to the interrogation group. • Experimental topical creams and lotions.

Document ID:	200202	Intravascular Ultrasound-Guided Intervention for Venous Leg Ulcers (IGuideU)		Classification:	For internal use
Modified:	13 Jan 2022	Clinical Investigation Protocol - ISO 14155		Author:	[name]
Version:	4.0	User Tool ID:	16.2.6UserTool0001	Page:	6 of 57
Status:	Final	User Tool Version Date:	08JUL2019		

Clinical Investigation Protocol

	
 Growth factors within first 3 months after randomization and within the first 3 months for subjects that crossover from the deferred-interrogation group to the interrogation group. 											
Schedule of Assessments	There are 6 in-person visits planned for this clinical study, including the screening visit. The study is anticipated to last a total of 24 months for each enrolled study											

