		Screening Visit	Baseline Visit/Index Procedure	1 Month (30 days)	3 Months (90 days)	6 Months (180 days)	12 Months (365 days)	18 Months (545 days)	24 Months (720 days)	Early Termination Visit*	Unscheduled Visit*	Re-intervention Procedure*
	Visit Window	-30 to 0 days	0 days	±14 days	±14 days	±30 days	±30 days	±30 days	±30 days	NA	NA	NA
	Visit Type	Office	Hospital/OBL	Office	Office	Office	Office	Phone Call	Phone Call	Office/Hospital/OBL	Office/Hospital/OBL	Hospital/OBL
	Informed Consent	X										
	Medical History	X										
	Eligibility/Inclusion and Exclusion Criteria	X										
	Urine Pregnancy Test ^a		X									
	Enrollment and Randomization	X										
	Duplex Ultrasound ^b			X	X	X	X					
	Physical examination	X		X	X	X	X			X	X	
	Anticoagulant and Antiplatelet	X	X	X	X	X	X	X	X	X ^h	X ^h	X ^h
	Clinical Laboratory Tests ^c		X									
	Venous Ulcer Assessment	X	X	X	X	X	X			X ^h	X ^h	X ^h
	Venous Ulcer Imaging		X	X	X	X	X			X ^h	X ^h	X ^h
	CEAP Clinical Category	X	X	X	X	X	X			X ^h	X ^h	X ^h
	VCSS Category	X	X	X	X	X	X			X ^h	X ^h	X ^h
	Study Visit Questionnaire			X	X	X	X			X ^h	X ^h	X ^h
	Wound Care Management Education ^d		X	X	X	X	X					
	SF-36		X							X ^h	X ^h	X ^h
EQ5D Questionnaire		X							X ^h	X ^h	X ^h	
Phone Call Questionnaire							X	X				
MPV Imaging ^e		X										

Document ID:	200202	Intravascular Ultrasound-Guided Intervention for Venous Leg Ulcers (IGuideU)		Classification:	For internal use
Modified:	13 Jan 2022	Clinical Investigation Protocol - ISO 14155		Author:	[name]
Version:	4.0	User Tool ID:	16.2.6UserTool0001	Page:	7 of 57
Status:	Final	User Tool Version Date:	08JUL2019		

[figure not shown]
Clinical Investigation Protocol

	IVUS Imaging ^e		X										
	Adverse Events ^f		X										
	Patient-completed Diary ^g SF-36 Questionnaire ^h EQ5D Questionnaire ⁱ	Completed monthly for study duration, through 24 months											

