
Abbreviations: CEAP - Clinical Etiology Anatomy Pathology, EQ5D – EuroQol 5 Dimensions; IVUS – intravascular ultrasound, MPV – multi- planar venography, SF-36 – Short form 36; VCSS – Venous Clinical Severity Score.
 
*Note: While an attempt should be made to collect all non-invasive testing at unscheduled visits, early termination visits, or re-interventions, a protocol deviation will not be required if all assessments are not completed.
 
^aUrine pregnancy test shall be taken on all females of childbearing prior to the index procedure.
 
^bIn all follow-up visits, DUS will be performed on the patients who received a stent implantation as part of the index procedure to assess stent patency and position.
 
^cClinical laboratory tests include: Serum creatinine and eGFR. These laboratory tests must be performed within 30 days of the index procedure.
 
^dStudy personnel will provide guidance on wound care management best practices according to the site/facility guidelines.
 
^eMPV and IVUS imaging will only be performed on patients receiving an index-procedure per the study protocol.
 
^fAdverse Event reporting is for peri-procedural events and IVUS-related adverse events (<48 after index-procedure).
 
^gSubjects will be provided with a diary at the baseline visit. The diary is designed to be completed on a monthly basis, as well as following any contact with the health care system related to treatment of his/her venous leg ulcer. The diary will be used to track major events, such as compliance to compression therapy and other notes related to the index ulcer. The diary also requires completion of the quality-of-life questionnaires (EQ-5D, SF-36). The diary will be reviewed at each office visit after the initial receipt. After the last in-person study visit, any hard-copy diaries will be sent to the study site coordinator on a monthly basis until the 24-month study completion.
 
^hFor early termination, unscheduled follow-up visits, and/or re-intervention procedures every attempt should be made to obtain the following assessments: Antiplatelet and Anticoagulant use; Study Visit Questionnaire; Venous Ulcer Assessment including venous ulcer imaging; CEAP clinical category, VCSS category, and the SF-36 and EQ5D Questionnaires.
 
ⁱ Questionnaires should be completed in the diary. If not completed in the diary, the subject should complete the questionnaires at the time of the visit.
 
^j Screening and baseline visits can be combined
													

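### The synopsis schedule ties adverse-event reporting and stent duplex scans to the index procedure and leaves re-intervention and crossover procedures unclear

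*Combined protocol and SAP*

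**What the plan says.** All references are to the Protocol Synopsis.

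- **Adverse events.** The row in the Schedule of Assessments has a single mark, under the baseline/index column. Footnote f describes reporting of peri-procedural and IVUS-related events, with a bracketed limit of 48 (no unit is printed) counted from the index procedure.
- **Duplex ultrasound.** The row is marked at months 1, 3, 6 and 12. Footnote b restricts it: "DUS will be performed on the patients who received a stent implantation as part of the index procedure".
- **Re-intervention.** The schedule has a column headed "Re-intervention Procedure". Footnote h lists what to try to collect there: antithrombotic use, visit questionnaire, ulcer assessment and imaging, CEAP, VCSS, SF-36 and EQ5D. An asterisk note on the column adds that "an attempt should be made to collect all non-invasive testing at unscheduled visits, early termination visits, or re-interventions", but also that "a protocol deviation will not be required if all assessments are not completed".
- **Crossover.** The Prohibit list under Test Groups restarts some of its three-month bans "for subjects that crossover from the deferred-interrogation group to the interrogation group". The schedule has no crossover column.
- **Related text.** Under Study Design, a medical monitor adjudicates serious adverse events around the procedure; which procedure is not said. Footnote e reserves venography and IVUS for patients who have an index procedure.

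**The concern.** The plan foresees three kinds of endovascular procedure: index, crossover and re-intervention. The rules for reporting harm and for following a stent are written around the first. A coordinator working from the schedule would find nothing to complete under adverse events at a re-intervention, and nothing in footnote h as a reminder. A bleed or vessel injury at a repeat procedure might then go unrecorded, or be recorded at some sites and not at others.

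The same dependence on the word *index* decides whether a stent placed later is scanned at all. Deferred patients stented at crossover could be followed differently from site to site, according to how each site reads the term.

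At stake are completeness and consistency of procedural safety data. The primary comparison of healing at 3 months is not affected.

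**Working it through.** The documents state no figure on this point, so the check is mainly a comparison of text.

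**1. Schedule against footnotes**

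| Item | Where marked | Procedure named in footnote | Marked under re-intervention | In footnote h |
|---|---|---|---|---|
| Adverse events (f) | Baseline/index only | Index | No | No |
| Duplex (b) | Months 1, 3, 6, 12 | Index | No | No |

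The table was read from PDF, so the position of one mark should not carry the argument alone. Here the mark, footnote f and footnote h all agree.

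**2. Does other text fill the adverse-event gap?**

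- The medical-monitor sentence says who adjudicates, not what sites must report. It also covers serious events only.
- The asterisk note concerns non-invasive testing. Reporting an adverse event is not a test, and the note is not binding.

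Neither clearly makes a re-intervention complication reportable.

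**3. Which stents does footnote b cover?**

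- Stented at index, later re-intervened: still covered at the remaining visits through month 12.
- First stented at a later, non-index procedure: not covered. The asterisk note may prompt a scan at the procedure or at an unscheduled visit, but requires none.
- First stented at crossover: depends on the reading. For a patient stented just after month 6:

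| Reading of crossover | Required scans |
|---|---|
| Not an index procedure | 0 |
| Index procedure, visits still counted from baseline | 1 (month 12) |
| Index procedure with its own day 0 | 4 (about months 6+1 = 7, 6+3 = 9, 6+6 = 12, 6+12 = 18) |

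An index stent at baseline also has 4. For a patient stented after the month-12 visit, the second reading gives 0, because months 18 and 24 are phone calls.

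**4. How many re-interventions?**

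Subject Population allows up to 266 patients randomised 1:1, so 266/2 = 133 per arm. Stenting and re-intervention rates are not given and are assumed here:

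- Stented, 40% to 80% of 133: 53 to 106.
- Re-intervened, 5% to 15%: 53 × 0.05 = 2.7 to 106 × 0.15 = 15.9, so about 3 to 16 patients.

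This indicates scale only.

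**The case against.** The other side has four fair arguments.

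- **Footnote f is wider than it looks.** The bracket may qualify only the IVUS-related events, leaving peri-procedural events at any procedure reportable. The medical-monitor sentence is likewise not confined to the index procedure. This stands to the extent that reporting at re-intervention is ambiguous, not shown to be excluded. It does not resolve the matter, since the blank cell and footnote h point the other way.
- **The asterisk note gives cover.** It plausibly reaches duplex, on a best-effort basis. It does not reach adverse events.
- **Crossover is already an index procedure.** Footnote e makes this the natural reading, because a crossover patient imaged under the protocol must be having one. The separate three-month count in the Prohibit list suggests a new clock too. This stands, and the remedy for crossover is simply to say so.
- **Only the synopsis was supplied.** Its page footers run to 9 of 57, and the Study Schematic is not reproduced. Fuller safety or crossover rules may exist. This stands and limits the point to the synopsis schedule. If such rules exist, the schedule should match them.

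**Conclusion.** The point holds as a gap in the synopsis schedule. Adverse-event reporting is anchored to the index procedure, and nothing in the supplied text clearly extends it to re-interventions. A stent first placed at a later non-index procedure has no required duplex, and the status and clock of a crossover procedure are not stated. The size is modest: about 3 to 16 re-intervened patients under the assumed rates, and between 0 and 4 required scans for the crossover example. Sample size, randomisation and endpoints are unaffected.

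A reader might infer more, but the documents do not support it:

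- *That re-interventions have no stent follow-up.* Footnote b keeps patients stented at index on duplex through month 12.
- *That a large share of first procedures escapes the safety rules.* This needs crossover not to be an index procedure, against the natural reading of footnote e.
- *That crossover scans follow the baseline clock.* No text says so; it is one of the possible readings.
- *That the reported complication rate would be too favourable.* The Endpoints section lists no complication rate, and no text shows that repeat procedures carry more risk.
- *That pre-procedure testing is deficient.* Footnotes a and c also name the index procedure, but the asterisk note plausibly reaches the urine test. The supplied text does not reach creatinine/eGFR at re-intervention, yet the synopsis alone cannot show that it would be omitted. No change is proposed there.

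**What to change.** 1. In footnote f, replace *index-procedure* with *any study endovascular procedure (index, crossover or re-intervention)*, and mark Adverse Events in the re-intervention column.
2. In footnote b, cover any stent placed during the study. For a stent placed at re-intervention this means the remaining duplex visits.
3. State that a crossover procedure is an index procedure and starts its own day 0 for adverse-event and duplex visits, as far as the patient's 24 months allow. Healing assessments for the randomised comparison should stay on the existing clock.

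The cost is amendment wording, a few more adverse-event forms using existing pages, and some later scans of a kind already specified for stented patients. Some scans will need added visits: for crossover at month 6, those due at about months 7 and 9 match no scheduled visit, and month 18 is a phone call. A full twelve-month duplex series fits within 24 months only if crossover occurs by month 12 (24 − 12 = 12).

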Endpoints	
Primary Clinical Endpoint The primary clinical endpoint is the difference in complete ulcer healing between the interrogation group and the deferred-interrogation group at 3 months. Complete ulcer healing is defined as 100% epithelialization of the venous ulcer. Healing will not be assumed for any area of the wound where a scab is present.
 
Diagnostic Endpoint The diagnostic endpoint is a composite of the difference in DVO detection and the subsequent changes in treatment plan created based on the IVUS information in combination with MPV information versus the initial treatment plan created using the information from MPV alone. DVO is defined as $\geq 50\%$ diameter reduction in the deep venous system when assessed by MPV or $\geq 50\%$ reduction in cross-sectional area (CSA) of the deep venous system when assessed by IVUS.
 
Changes in the following parameters will be considered a changed in treatment plan:
 
 1. Location of the IVC confluence (common iliac vein/confluence interface) relative to vertebral bodies 2. Presence of significant disease ($\geq 50\%$ reduction in diameter and/or cross-sectional area) 3. Location of the disease

Document ID:	200202	Intravascular Ultrasound-Guided Intervention for Venous Leg Ulcers (IGuideU)		Classification:	For internal use
Modified:	13 Jan 2022	Clinical Investigation Protocol - ISO 14155		Author:	[name]
Version:	4.0	User Tool ID:	16.2.6UserTool0001	Page:	4 of 57
Status:	Final	User Tool Version Date:	08JUL2019		

Clinical Investigation Protocol

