	
 4. Percentage (%) of obstruction/compression (compression or residual lumen diameter divided by reference vessel diameter) 5. Reference vessel and associated diameter/CSA 6. Length of disease (mm) 7. Decision to stent 8. Decision to pre- and/or post-dilate the occlusion 9. Number of stents to be used 10. Length(s) and Diameter(s) of stents to be used 11. Manufacturer and model of stent(s) to be used 12. Desired landing zones for stent placement 13. Diagnosis of PTS, NIVL, or other 
Secondary Endpoints The following are secondary endpoints:
 
 1. Rate of ulcer healing measured between groups at 3, 6, 12, 18 and 24 months. 2. Rate of ulcer healing for stented PTS and NIVL patients at 3, 6, 12, 18 and 24 months. 3. Recurring ulcers in both arms from 3 months out to follow-up visit 24 months provided each arm has at least 30 subjects. The choice of 30 is based on central limit theorem in order to have normally distributed data for descriptive summary statistics. 4. Recurring ulcers between PTS and NIVL sub-groups. 5. Change in QoL using EQ5D and SF-36 forms. 6. Change in clinical score will be assessed using the VCSS and CEAP scoring systems. 7. Medical resource utilization (MRU) and health economic analysis between the interrogation and deferred-interrogation arms. 
*Note: Every effort will be made to balance the enrollment of PTS and NIVL patients.

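### Adverse event reporting in the synopsis is tied to an index-procedure window with no unit, so adverse events cannot be compared by randomised arm over the 24 months of follow-up

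*Combined protocol and SAP*

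**What the plan says.** All references are to the Protocol Synopsis.

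- **Schedule of Assessments, footnote f:** "reporting is for peri-procedural events and IVUS-related adverse events (<48 after index-procedure". No unit follows the number.
- **Schedule of Assessments, row "Adverse Events ^f":** one mark, in the Baseline Visit/Index Procedure column. There is none at months 1 to 24, nor in the early termination, unscheduled or re-intervention columns. Footnote h, which lists what to attempt at those last three, does not include adverse events.
- **Study Design:** "The study will also utilize a medical monitor to review and adjudicate peri-procedural serious adverse events (SAE".
- **Endpoints:** "The primary clinical endpoint is the difference in complete ulcer healing between the interrogation group and the deferred-interrogation group at 3 months"; "The diagnostic endpoint is a composite of the difference in DVO detection and the subsequent changes in treatment plan". The seven secondary endpoints cover healing (two), recurrence (two), quality of life, clinical scores, and lastly "Medical resource utilization (MRU) and health economic analysis between the interrogation and deferred-interrogation arms". None is a safety outcome.
- **Footnote b:** at follow-up, "DUS will be performed on the patients who received a stent implantation as part of the index procedure to assess stent patency and position". The schedule places this duplex at months 1, 3, 6 and 12.
- **Footnote e:** venography and IVUS are done only in patients who have an index procedure.

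**The concern.** The trial compares a strategy that may leave a permanent implant with one that defers it. A secondary objective is long-term clinical and economic impact, and healing is compared between arms out to 24 months. A reader of the results will want to weigh that benefit against harm over the same period and between the same randomised groups.

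The AE rule does not allow this. It starts from an index procedure, which deferred patients do not have unless they cross over, and it ends soon after that procedure. Late deep vein thrombosis or pulmonary embolism (DVT/PE) and bleeding have no scheduled AE record in either arm, although antithrombotic use is recorded to month 24. Events not collected prospectively in both arms would have to be reconstructed from records afterwards, which is rarely complete or even-handed. The missing unit also lets sites apply different windows.

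**Working it through.** The documents state no safety figure to reproduce, so the check is mainly a reading of passages side by side.

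**1. Who is covered.** Footnote f counts from the index procedure, and footnote e links the study imaging to that procedure.

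- Interrogation arm: an AE window opens at the index procedure.
- Deferred arm, no crossover: no index procedure, so no window and 0 scheduled days.
- Deferred arm, crossover (foreseen under Test Groups): a window may open at the later procedure. These patients are selected after randomisation, so their events cannot stand in for the whole arm.

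A comparison of AE rates by randomised arm is therefore not available from the scheduled reporting.

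**2. How long it lasts.** The last visit is scheduled at day 720. Share of follow-up covered = window in days / 720. The unit is an assumption:

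| Unit assumed | Days | Share of 720 days |
|---|---|---|
| hours | 48/24 = 2 | 2/720 = 0.28% |
| days | 48 | 48/720 = 6.67% |
| weeks | 48 × 7 = 336 | 336/720 = 46.67% |

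On every reading most of follow-up lies outside the window. These are shares of calendar time, not shares of harm missed.

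**3. What the window governs.** Footnote f can be read two ways. Either the limit applies to both kinds of event, or only to the IVUS-related ones. On the second reading the peri-procedural period has no stated length at all.

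**4. What else is collected.**

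| Source | Period | Who | What it leaves open |
|---|---|---|---|
| Duplex | months 1, 3, 6, 12 | stented at index | no endpoint or AE category uses it |
| Re-intervention visit column | as needed | as they occur | no AE mark, no named summary |
| Physical examination | months 1 to 12 | no arm limit stated | not an event record |
| Antithrombotic use | to month 24 | no arm limit stated | exposure, not bleeding |
| Monthly diary | to month 24 | no arm limit stated | centred on the index ulcer |
| Resource utilisation | components not listed in the synopsis | compared by arm | may count re-interventions, not adjudicated events |

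**5. Scale, by assumption only.** The documents give neither a stenting rate nor a late-event rate. With 212/2 = 106 evaluable patients in the interrogation arm and an assumed late-harm risk of 1% to 10%, the expected count is 106 × 0.01 = 1.1 to 106 × 0.10 = 10.6. This is not an estimate of undetected harm, because duplex would show some of these events.

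**The case against.** The strongest reply is that only the synopsis is available, pages 4 to 9 of 57. AE definitions, serious event and device-deficiency reporting, and the monitor's full remit normally sit in the body. This stands as a limit: nothing here shows that the whole protocol lacks wider rules. It does not remove the point, because in that case the synopsis contradicts the body.

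Two stronger readings are tempting, and the documents do not support either.

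- **A reader might infer that late stent harm is never counted.** Scheduled duplex looks for loss of patency and change of position up to month 12, and re-intervention has its own visit column. What is missing is a named summary of these findings.
- **A reader might infer that the deferred arm has no safety data.** Examinations, antithrombotic records, the diary and resource use are not confined to one arm. What is missing is scheduled AE reporting.

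It can also be said that hours is the natural unit for a peri-procedural window, that stenting is on-label, and that the stated objectives are healing, diagnostic change and long-term impact. The first is probably right and makes the unit a drafting correction. The other two explain why safety is not a primary question. They do not explain why harm should be left incomparable by arm when benefit is compared to month 24. Making patency a formal endpoint goes further than the gap requires; a tabulation is enough.

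**Conclusion.** The point holds in a limited form and should be fixed. The AE row, footnote f and the monitor's remit (to "review and adjudicate peri-procedural serious adverse events (SAE") agree with one another, so this is unlikely to be an artefact of table extraction. Followed as written, the synopsis schedules no AE reporting for deferred patients who do not cross over and none for anyone after the window, and no named safety summary picks up late duplex or re-intervention findings.

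The measurable size is the window's share of follow-up, and it rests on the assumed unit. The number of patients affected cannot be derived. The conclusion also assumes that the unseen protocol body does not already require wider reporting.

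**What to change.** 1. State the unit in footnote f and which events the limit applies to, and keep it as the peri-procedural sub-window.
2. Amend footnote f and the Adverse Events row to record serious adverse events and a short pre-named list in both arms from randomisation to month 24: death, DVT/PE, stent occlusion or migration, major bleeding, ulcer infection with admission, amputation. Ask at the visits and phone calls already scheduled.
3. Summarise these events descriptively by randomised arm.
4. Tabulate the duplex patency and position results and the re-interventions already collected in stented patients.
5. Extend the medical monitor's review to these serious events.
6. If the protocol body already has wider AE rules, reconcile the synopsis with them.

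**Cost:** a protocol and case report form amendment, more event reporting by sites and more review by the monitor. It needs no new visit, imaging or patient.

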
Subject Population
	
In order to have 212 evaluable subjects with a 20% projected attrition rate, up to 266 evaluable subjects will be enrolled and randomized.
 
Inclusion Criteria:
 
 1. Be ≥ 18 and ≤ 85 years of age. 2. Able and willing to participate and comply with the protocol, including the defined follow-up schedule, by signing an IRB or Ethics Committee approved informed consent form. 3. Active venous leg ulcer (CEAP C6). 4. Previously completed treatment for clinically significant reflux in the superficial and/or perforator venous system of the target limb ≥ 3 months prior to enrollment, if clinically indicated. 5. Completed at least 3 months of prescribed compression therapy after any ablation. 6. Palpable dorsalis pedis or posterior tibial artery (DP/PT) pulses at ipsilateral foot or ABI ≥ 0.8. 7. Be able to ambulate unassisted or with non-motorized assistive devices. 8. Current VLU present ≤ 48 months. 
Exclusion Criteria:
 
 1. Patient is known pregnant or breast-feeding or planning to become pregnant in the following year. 2. If antiplatelet and anticoagulation therapy cannot be tolerated. 3. Previous venous stent implantation involving the target limb, target lesion, or inferior vena cava. 4. Previous venovenous bypass surgery involving the target limb. 5. Previous endovascular recanalization of the target lesion segment 6. Known metal allergy precluding stent implantation.

Document ID:	200202	Intravascular Ultrasound-Guided Intervention for Venous Leg Ulcers (IGuideU)		Classification:	For internal use
Modified:	13 Jan 2022	Clinical Investigation Protocol - ISO 14155		Author:	[name]
Version:	4.0	User Tool ID:	16.2.6UserTool0001		
Status:	Final	User Tool Version Date:	08JUL2019	Page:	5 of 57

Clinical Investigation Protocol

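### The primary 3-month healing read-out has no stated time origin: its visit is counted from baseline/index procedure, up to 30 days after randomisation, and nothing in the supplied synopsis makes that gap equal between arms

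*Combined protocol and SAP*

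**What the plan says.** In the Protocol Synopsis, Schedule of Assessments, the row "Enrollment and Randomization" is marked only under the screening visit, whose window is -30 to 0 days. Day 0 is a single column for both arms, "Baseline Visit/Index Procedure", with visit type hospital/OBL. The 3-month visit is day 90 ±14 on that scale. Footnote j states "Screening and baseline visits can be combined" and does not limit this to one arm. Footnote e confines the venography and IVUS imaging to patients who have an index procedure.

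Under Test Groups, the deferred-interrogation arm "will continue to receive non-invasive therapies consisting primarily of compression therapy/stockings", so before any crossover it has no procedure to date.

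The Primary Clinical Endpoint is the "difference in complete ulcer healing between the interrogation group and the deferred-interrogation group at 3 months". No starting point for the 3 months is given. Elsewhere the synopsis does name one: under Test Groups, the prohibitions on grafting, skin substitutes and growth factors run for 3 months from randomisation.

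**The concern.** The primary endpoint is a proportion healed at a fixed time, so it is only comparable if that time is the same in both arms when measured from randomisation. Here day 0 is set after allocation. In the interrogation arm it is tied to a catheter procedure that needs a hospital or OBL slot. In the deferred arm nothing supplied ties it to any event, and footnote j lets it coincide with the screening and randomisation day.

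If interrogation patients wait longer on average for day 0, their ulcers have more time under compression before the read-out. Closures during that wait count as treatment effect even if interrogation does nothing. Randomisation does not balance an interval that is fixed after allocation. The ±14-day window does not help either, because it applies around whichever day 0 was used and leaves a systematic shift in place.

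**Working it through.** **Sample size.** The Subject Population section states: "In order to have 212 evaluable subjects with a 20% projected attrition rate, up to 266 evaluable subjects will be enrolled and randomized". With 1:1 allocation (Study Design), 212/2 = 106 evaluable per arm. Allowing for 20% attrition, 106/0.80 = 132.5, rounded up to 133, and 2 × 133 = 266. The figure reproduces, so 106 per arm is used below. The 212 itself cannot be checked, because the supplied pages give no healing rates, power or alpha.

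**Time from randomisation to read-out.** Let w be the days from randomisation to day 0. The screening window gives w = 0 to 30, in either arm. The nominal read-out is at 90 + w, that is 90 to 120 days after randomisation, before the ±14-day window is applied. The largest possible between-arm difference is 120 - 90 = 30 days, or 30/90 = 33% more healing time.

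**Effect on the primary comparison.** The documents give neither a healing rate nor an actual wait, so these are assumptions: no true treatment effect, a constant healing hazard, p healed at day 90 in the deferred arm (20%, 40% or 60%), 106 per arm, and a two-sided 5% pooled z-test. Let g be the extra days in the interrogation arm.

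- Healed proportion with g extra days: q = 1 - (1 - p)^((90 + g)/90)
- With m = (p + q)/2: SE0 = √(2m(1 - m)/106) and SE1 = √((p(1 - p) + q(1 - q))/106)
- Probability of rejection = Φ((q - p - 1.96·SE0)/SE1) + Φ((-(q - p) - 1.96·SE0)/SE1)

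Worked example, p = 0.40 and g = 14: q = 1 - 0.60^(104/90) = 0.446, a gain of 4.6 points. SE0 = 0.0679 and SE1 = 0.0678, so rejection = 0.099 + 0.004 = 0.103.

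| Extra days g | p = 20% | p = 40% | p = 60% |
|---|---|---|---|
| 7 | 21.4% (+1.4 points; rejection 5.7%) | 42.3% (+2.3; 6.4%) | 62.8% (+2.8; 7.0%) |
| 14 | 22.7% (+2.7; 7.7%) | 44.6% (+4.6; 10.3%) | 65.3% (+5.3; 12.5%) |
| 30 (ceiling) | 25.7% (+5.7; 16.8%) | 49.4% (+9.4; 27.9%) | 70.5% (+10.5; 36.2%) |

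If interrogation waits were spread evenly over 0 to 30 days and deferred patients had no wait, the mean gain would be 2.9 to 5.5 points, close to the 14-day row. With both arms read at the same time from randomisation, g = 0 and the gain is zero.

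**The case against.** A reader might infer that interrogation ulcers do get up to 30 extra days, and that the false-positive rate is therefore about 28% (the 40% case). The documents do not support that.

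- The -30 to 0 window, the single baseline column and footnote j apply to both arms. An interrogation patient may have a same-day baseline, and a deferred patient may have one 30 days after screening.
- The synopsis plans 6 in-person visits including screening. The schedule gives screening, baseline and months 1, 3, 6 and 12, so a separate baseline visit is the default for everyone.
- Deferred patients also have baseline work: ulcer imaging, quality-of-life questionnaires, wound-care education and issue of the diary.
- Laboratory tests need not add a wait, since footnote c accepts them within 30 days of the procedure.
- Thirty days is a limit for one patient. The 28% requires every interrogation patient to wait 30 days and no deferred patient to wait at all.
- Eligible ulcers are still open after at least 3 months of prescribed compression (inclusion criterion 5), so the lower assumed healing rates are at least as plausible as the higher ones.
- The supplied text stops at page 9 of 57 and the schematic is not shown. A rule dating the deferred baseline, or an analysis that counts from randomisation, may exist elsewhere.

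All of this stands, and it removes any claim that a bias of known size is present. It does not remove the gap in the plan: the synopsis uses two origins for 3 months, names neither for the primary endpoint, and ties day 0 to a procedure in only one arm.

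**Conclusion.** The concern holds as a missing common time origin for the primary endpoint, with a plausible direction. Following the schedule as supplied can give the arms unequal healing time before the read-out. A longer wait in the interrogation arm is an inference from who has a procedure to book, and if it occurs it favours that arm. The likely size depends on the mean between-arm gap, which the documents do not give. Gaps of 7 to 14 days would add 1.4 to 5.3 points and put the false-positive rate at about 6% to 13%. The 17% to 36% at 30 days is a ceiling and not an expectation. These figures rest on a constant hazard, no true effect, 20% to 60% healed at day 90, 106 per arm and a two-sided 5% test.

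This should be fixed before the primary analysis. It is hard to repair afterwards, because healing status at a common day may not have been observed.

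**What to change.** State one origin for the primary healing read-out and apply it in both arms. Either of these would do:

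1. Assess healing at day 90 ±14 from randomisation for every patient.
2. Set day 0 by the same rule in both arms. For example, assign every patient a planned baseline date before allocation is revealed, and count the healing visits from that date whatever happens to the procedure.

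Under either option, keep post-procedure checks on the procedure clock. Footnote b requires duplex of stented patients at all follow-up visits. A 1-month visit moved to a randomisation clock (day 30 ±14, so day 16 to 44) could precede a procedure done up to day 30. Report days from randomisation to baseline and to read-out by arm. The text should also reconcile the 3 months used for the wound-therapy prohibitions, counted from randomisation, with the 3 months used for the visit. As written, a patient with a 30-day gap leaves the prohibited period about 30 days before the nominal read-out.

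Cost: wording in the endpoint definition and schedule, and a change to the visit-date calculator. Under option 1, the healing window is day 76 to 104 from randomisation and the 3-month duplex window is day 76 + w to 104 + w. The two overlap whenever w ≤ 28, so one visit can nearly always serve both. The real downside of option 1 is that interrogation patients have up to 30 fewer post-procedure days at the nominal read-out (60 instead of 90 at the extreme), so the observed effect may be smaller. Option 2 avoids a systematic loss of this kind if procedures take place on the planned date, but it needs that date fixed and recorded before allocation is known.
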